We also define Study Days in the LTE14762 study as the number of days from first significant dose in LTE14762 and calculate similarly as the Treatment Days. For participants who received first significant dose in LTE14762, the Study Days is the same as the Treatment Days.

For participants under the revised dose and regimen, both efficacy and safety data will be analyzed from the dose re-start Day 1 up until the last day of study follow-up.

Treatment day after the dose re-start will be calculated as evaluation date – first dose date after dose re-start + 1 (days). It should be not applicable for assessments before the dose re-start. A summary of study periods and start day in analysis is outlined in [Figure 1](#)

Figure 1 Study periods and analysis start day summary

	Original dose and regimen	2017 clinical hold/2020 voluntary dose pause	Revised dose and regimen
Efficacy analysis	Starts from first significant dose of fitusiran in TDR14767(ALN-AT3SC-001) or LTE14762 and in terms of treatment days.	Starts from the 29th days after last dose date before the hold/pause	Starts from first dose date of revised dose and regimen and in terms of treatment days
Safety analysis	Starts from first significant dose of fitusiran in LTE14762 and in terms of study days	Starts from the day after last dose date before the hold/pause and in terms of study days	Starts from first dose date of revised dose and regimen and in terms of study days

Summary statistics will be reported by analysis visits defined in [Section 5.10](#) below. Unless otherwise noted, tables under both the original and revised dose regimens will be presented by hemophilia type, inhibitor type and overall. Participants who received a significant dose in TDR14767(ALN-AT3SC-001) will be considered as a subgroup in the analysis under the original dose and regimen. Details will be specified in the [Section 6.11](#).

Categorical data summary will include the number and percentage of participants within each category, with a category for missing data. Continuous data summary will include descriptive statistics - the number of participants, mean, median, standard deviation (SD), first quartile (Q1), third quartile (Q3), minimum, and maximum. The precision of the measurement for each continuous variable will be used to determine the number of decimal places to present in tables, figures and derived listings. Minimum and maximum values will be reported with the same

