6.2 DEMOGRAPHICS AND BASELINE CHARACTERISTICS

Demographics and baseline disease characteristics will be summarized for the safety analysis set 1 and safety analysis set 2. Demographics will include age, age group, gender, race, ethnicity, height, weight, body mass index (BMI), and region. Baseline hemophilia disease characteristics will be reported from parent study TDR14767(ALN-AT3SC-001) and will include hemophilia type, biological phenotype, historical ABR based on 6-month bleed history prior to parent study entry and historical number of hemophilia clinic visits.

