6.3.1 Analysis of long-term durability and efficacy

6.3.1.1 Annualized bleeding rate

The ABR efficacy analysis will include all bleeding events occurring in the efficacy period. The ABR will be annualized for each participant using the following formula:

$$\text{Annualized bleeding rate (ABR)} = \frac{\text{total number of bleeding events}}{\text{total number of days in the respective period}} \times 365.25$$

The primary efficacy analysis will consist of the ABR results based on the “on-treatment strategy” during the efficacy period (efficacy period as strictly defined in [Section 6.3](#) above, excluding the periods of intercurrent events). The “on-treatment strategy” analysis will also be performed for the onset period and the treatment period. The “treatment policy strategy” analysis, will be performed for the treatment period only, and will consist of the ABR calculations applied to *all* (treated) bleeds (even including surgery periods), taking place during the analysis period of interest only excluding the gap between TDR14767(ALN-AT3SC-001) and LTE14762 where the bleeds were not collected. ABR will be estimated (with 95% CI) using a negative binomial model adjusted by TDR14767(ALN-AT3SC-001) study baseline ABR. No imputations of missing data will be performed in the ABR analyses. The ABR analysis under the original dose and regimen will be performed for the entire efficacy period 1 and also for the treatment period 1 and onset period (for the “on-treatment strategy”), as well as by year for the treatment period 1 (both on-treatment and treatment policy strategies) in order to demonstrate the durability of the prophylactic maintenance. Model based ABR will be provided when there are at least 3 participants in the group and model converges for by-year analysis. Also, additional analyses will be performed including all bleeds, both “treated” and “untreated”.

ABR under the revised dose and regimen after the dose pause for treated bleeding events and all bleeding events during the dose adjustment period, efficacy period 2 and treatment period 2 based on on-treatment strategy will be analyzed respectively. ABR for treated bleeding events during the treatment period 2 will also be summarized based on on-treatment strategy every 6 months. Similar ABR analysis during treatment period 2 based on treatment policy (ignoring all intercurrent events) will be performed as well.

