6.11 SUBGROUP ANALYSIS

Participants who received their significant dose in parent study will be considered as a subgroup for below endpoints. These subgroup analyses only applicable for the analyses under the original dose and regimen.

- Annualized bleeding rate (ABR) during the efficacy period for treated bleeds and all bleeds
- Annualized weight-adjusted consumption of FVIII, FIX and BPA
- Quality of life (QoL) measured by EuroQol 5-dimension 5-level (EQ-5D-5L) score
- QoL measured by Haem-A-QoL score
- AT activity level
- TG level

Negative binomial regression model will be applied only for subgroup that has at least 3 participants and the model converges. Otherwise, only summary statistics will be presented.

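### The SAP lets a three-parameter negative binomial ABR model with a 95% CI be reported in as few as three participants, where the interval's coverage is unreliable

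*SAP*

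**What the plan says.** SAP 6.3.1.1 specifies the estimator: "ABR will be estimated (with 95% CI) using a negative binomial model adjusted by TDR14767(ALN-AT3SC-001) study baseline ABR". The analysis of the original regimen covers the whole efficacy period, the treatment and onset periods, "as well as by year for the treatment period 1", and the stated aim is "in order to demonstrate the durability of the prophylactic maintenance". The release rule for the by-year results is: "Model based ABR will be provided when there are at least 3 participants in the group and model converges for by-year analysis".

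SAP 6.11 has a matching rule for its one subgroup, participants who had a significant dose in the parent study: "Negative binomial regression model will be applied only for subgroup that has at least 3 participants and the model converges". It adds a fallback: "Otherwise, only summary statistics will be presented". SAP 6.3.1.1 states no such fallback for the by-year analysis.

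SAP 5.2 sets the general layout: "tables under both the original and revised dose regimens will be presented by hemophilia type, inhibitor type and overall". The SAP does not define convergence, does not say what happens when the dispersion is estimated at zero, does not name the type of confidence interval, and gives no small-sample correction. For the whole-period ABR analyses it states no minimum group size.

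**The concern.** A negative binomial model with one continuous covariate has three parameters. At the permitted minimum there are three participants. Two of the parameters describe the mean, which leaves 3 − 2 = 1 residual degree of freedom from which to learn the between-participant variation. If the dispersion is then estimated at zero, the reported interval is a Poisson interval, which ignores that variation. An optimizer can reach such a solution without difficulty, so an undefined convergence condition may let it through.

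The by-year figures are meant to show that the effect lasts. If an interval printed as 95% covers 60% to 80% of the time in a thin late year, a reader will think durability is better known than it is.

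**Working it through.** **Figure to reproduce.** There is none. Neither document gives an expected ABR, a dispersion, a power calculation or an expected precision. Protocol 10.1 says the study size does not rest on a power analysis.

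**Inputs from the documents**
- Model, covariate and confidence level: SAP 6.3.1.1.
- Minimum group of 3: SAP 6.3.1.1 (by year) and 6.11 (subgroup).
- Follow-up in a by-year fit: at most about one year per participant.
- Covariate: "historical ABR based on 6-month bleed history prior to parent study entry" (SAP 6.2). Its distribution is not given.
- Size for comparison: up to 48 planned (Protocol 10.1); 13 + 21 = 34 participants by dose in August 2017 (Protocol 1.3.3).

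**Assumed inputs (not in the documents)**
- True ABR 0.5 to 15 per year; dispersion k of 0.5, 1 or 2; follow-up of 1 year each.
- Baseline ABR gamma with shape 1.5 and mean 20; log-rate slope 0 or 0.02 per bleed per year.
- Wald interval on the log scale.

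**Model.** Count Y with mean μ and variance μ + kμ², where log μ = log(years) + β0 + β1(baseline − group mean). Interval: exp(β0 estimate ± 1.96 × SE). Parameters: β0, β1, k, so 1 + 1 + 1 = 3.

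**Why a zero dispersion estimate matters.** Ignoring the slope, the variance of the log rate with n participants and one year each is about (1/μ + k)/n. A Poisson fit uses (1/μ)/n. The standard error is then too small by a factor of about √(1 + kμ). With k = 1 this is √1.5 = 1.22 at ABR 0.5, √3 = 1.73 at ABR 2 and √11 = 3.32 at ABR 10. This is a large-sample approximation. It shows why the problem grows with the rate, not how large it is at n = 3.

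**Simulation at n = 3.** Maximum-likelihood fits, 1,500 to 2,000 datasets per scenario. Coverage is among usable fits (SE of log ABR below 5). Ranges are over k and, where both were run, slope. A dash means not tabulated.

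| True ABR | Usable fit | Dispersion estimated at 0 (of usable fits) | Coverage of nominal 95% CI | Median upper/lower limit ratio |
|---|---|---|---|---|
| 0.5 | 34–46% | 77–89% | 91–96% | – |
| 1 | 51–66% | – | 93–95% | 13–17 |
| 2 | 67–89% | 64–84% | 92–95% | – |
| 3 | – | – | 89–92% | 5–10 |
| 6 | 85–99% | 53–69% | 66–78% | 3.5–7.9 |
| 10 | 90–100% | 44–58% | 58–70% | – |
| 15 | 94–100% | 38–52% | 55–64% | – |

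Separate runs at ABR 5, including some with a log-normal baseline (median 15), gave about 70% to 83%. The fitting routine was checked against a standard package on one dataset of 34: log ABR 1.2271 in both, SE 0.200 against 0.201.

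**Larger groups** (ABR 1, 3 and 6; k 0.5 to 2; slope 0.02)

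| n | Coverage |
|---|---|
| 5 | 74–97% |
| 10 | 83–95% |
| 20 | 89–94% |
| 34 | 92–94% |

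**Two possible repairs at n = 3.** Replacing 1.96 by the t quantile with n − 2 = 1 degree of freedom gives 99.9% to 100% coverage, so it overcorrects. Counting only fits with non-zero dispersion as converged gives 87% to 96% (ABR 1 to 6), but few fits survive: at ABR 6 and k = 2, about 40% of datasets.

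**The case against.** **Low rates.** If on-treatment bleeding is rare, coverage is close to nominal, and nothing in the documents says the rate will be high. This stands, and it rules out an unconditional claim of poor coverage. It does not rescue the rule: at ABR 1 only 51% to 66% of datasets give a usable fit, and the median upper limit is 13 to 17 times the lower.

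**Convergence might already screen out the bad fits.** It would help if fits with zero dispersion were treated as failures. The SAP does not say so, so the outcome depends on programming choices.

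**Small cells may be rare.** A reader might infer that groups of three will be common. The documents give no cell counts. SAP 5.2 does not say that hemophilia type and inhibitor type are crossed, and SAP 6.11 concerns a single subgroup. Protocol 1.3.3 shows 34 participants by dose in August 2017 and 6 + 11 = 17 inhibitor patients in parent-study Part D. Very small cells are possible, for example in late years, but their frequency is unknown.

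**The analyses are descriptive.** No hypothesis test depends on these intervals, participant-level ABR is calculated and data are listed. This limits the consequence. It does not make a mislabelled 95% interval acceptable in the analysis meant to show durability.

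**An unadjusted rate with a robust variance and t(n − 1) interval is a tempting substitute.** Its coverage is better, but at n = 3 and k = 1 its median upper/lower ratio is about 144 at ABR 2 and 74 at ABR 10. It would also mix adjusted and unadjusted quantities within one by-year series.

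**Conclusion.** The point holds in a limited form. The by-year and subgroup rules release a three-parameter model at three participants, and the only other safeguard is undefined. Under the assumptions above, coverage of the nominal 95% CI at that size runs from about 55% to 96%. It is near nominal at 2 or fewer bleeds per year, about 70% to 83% at 5, and about 58% to 70% at 10. Between 38% and 89% of usable fits give a Poisson interval although the simulated counts are overdispersed.

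Two stronger readings are not supported. One is that the interval always covers far less than 95%: that holds only from roughly 5 bleeds per year, and the rate, the dispersion and the Wald form are all assumed. The other is that the whole-period ABR result is undermined: the three-participant by-year rule does not govern it, and at n = 34 simulated coverage is 92% to 94%.

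**What to change.** In SAP 6.3.1.1 (by-year) and 6.11:

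- Raise the minimum group size for the model-based ABR and its CI well above three, for example to at least 10 and preferably about 15 to 20. The exact cut-off is a judgement: coverage is still 83% to 95% at 10 and 89% to 94% at 20.
- Below the minimum, give descriptive statistics only: participant-level ABR and the crude rate, total events / total days × 365.25. This extends the existing SAP 6.11 fallback to the by-year analysis.
- Define convergence, and state that a fit with dispersion estimated at zero does not count as a converged negative binomial model.

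The cost is SAP wording and a few lines of code. Small cells lose their model-based interval. A larger group whose counts happen to look Poisson would lose it too. At n = 10 and ABR 6 that affected only about 1% to 2% of simulated fits (k = 1 and 2).

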6.3.1.2 Bleed-free duration

Bleed-free duration (BFD) for each participant will be calculated as the time interval between 2 protocol-defined treated bleeding events, excluding bleeding events that occur during the intercurrent periods during both of the efficacy periods based on on-treatment strategy respectively. If participant don’t have any bleeding event in each of the efficacy period, the overall duration of the corresponding efficacy period will be the bleed-free duration. ABR and maximum BFD (after 1st significant dose) will be summarized descriptively. A similar calculation

of bleed-free duration considering all bleeding events will be performed for clinical hold or voluntary dose pause analysis described in [Section 6.5](#).

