- a This schedule applies for patients meeting criteria for adjusted dosing regimen. Upon each dose adjustment, the patient will restart the schedule (For dose adjustment from 50 mg Q2M to 50 mg QM, the patient will restart at PR M1 as their Month 6 visit under 50 mg will serves as their PR Study Day 1. For dose adjustment from 50 mg QM to 80 mg QM, the patient will restart at PR Study Day 1). The duration that the patient must continue in the study post modified IMP dose/frequency re-start depends on the re-start time-point relative to the overall study start for each individual patient to ensure an overall duration of fitusiran administration of approximately 72 months or 18 calendar months after restarting dosing post dosing pause (whichever is longer). Thus, when the patient reaches the latter of 72 months of study participation or 18 calendar months post dosing restart, the EOT visit should be performed, followed by the EOS and AT follow-up period.
- b Patients will follow either the Q2M or QM dosing regimen according to the dose adjustment rules; see Section 6.5.1.3. SC administration of study drug as per Pharmacy Manual. From Year 3 onwards, the frequency of predose LFT monitoring may be decreased for patients who have negative hepatitis C antibody titers and meet specific criteria defined in Section 6.5.1.1.
- c On Day 1, a directed physical examination will be performed at predose and 6 hours postdose. On all other dosing days checked in the table, the directed physical examination will be performed predose. See Section 9.1.5 for assessments to be performed during a directed physical examination.
- d Vital signs include blood pressure, heart rate, body temperature (oral, tympanic, or axillary), and respiratory rate. Vital signs will be measured in the seated or supine position after the patient has rested comfortably for 10 minutes. On Day 1, vital signs will be collected predose and at 6 hours (±30 minutes) postdose. On all other dosing days checked in the table, vital signs will be collected predose.
- e 12-lead ECGs will be performed in the supine position after the patient has rested comfortably for 10 minutes. 12-lead ECGs will be performed before blood sample collection.

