10.2.3 Efficacy Analyses

Annualized bleed rate estimate will be calculated as the number of bleed events occurring 4 weeks after the first dose of fitusiran in this study and until the End of Study visit. Bleed-free duration will be defined as the maximum time intervals between 2 bleeding events and will be analyzed descriptively. Bleed rate reduction and percentage reduction compared with pretreatment will also be calculated.

A weight-adjusted consumption of FVIII or FIX or BPA will be assessed.

Patient-reported QoL will be assessed by descriptive statistics for the EQ-5D-5L questionnaire. Descriptive statistics will be provided for observed values and changes from baseline (ie, Day 1, predose in the current study).

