2.6 OTHER MODIFICATIONS MADE TO THE STATISTICAL ANALYSIS PLAN

This section summarizes other changes to the SAP during this amendment, based on interpretation of the Protocol.

Other SAP amendment changes

Description of change to SAP	Reason for revision
Kaplan-Meier (Time-to-event) analyses deleted from SAP Section 6.5.	The protocol specifies only that the times between successive bleeds be summarized descriptively.
Replace lab analysis using CTCAE by PCSA. Lab analysis by NCI CTCAE grade and shift tables are removed in Section 6.8.3 since PCSA analysis will be performed. Vital sign by PCSA is added in Section 6.8.4 .	To be aligned with Sanofi's standard analysis for Lab and vital sign.
Treatment period is defined to be the onset period plus the efficacy period.	The term "treatment period" is defined in Section 6.3 for consistency with other Fitusiran studies.
The 'treatment policy strategy' of analyzing the ABR is added to the primary analysis.	Added in Section 6.3.1 for consistency and comparison with other Fitusiran studies.
In the LTE14762) study we will consider untreated bleeds as well as treated bleeds in efficacy analyses.	Modifications made to Section 6.3 to the effect that additional analyses will be performed which will include all bleeds, both treated and untreated.
Concomitant medication was removed from safety variables in Section 3.2.4 .	Typo corrected.
'Patient' was replaced by 'participant' throughout the document except for description of study design.	Align with company standard.
Analysis sets are defined for participants receiving original dose and regimen and participants receiving revised dose and regimen separately. Covid unaffected sets and full analysis sets are described in Section 4 .	Treatment regimens are different before and after the dosing pause in 2020. Analysis sets are refined accordingly. Inclusion of covid unaffected sets to evaluate the impact of pandemic on the study. Inclusion of full analysis sets for efficacy analysis.

Description of change to SAP	Reason for revision
Description of intercurrent events is updated in Section 6.3..	Inclusion of 2020 voluntary dose pause. Update the definition of missing 2 consecutive dose for revised dose and regimen.
An additional baseline defined for safety analysis after the 2020 dosing pause.	Given the duration of voluntary dose pause in 2020, an additional baseline for selected safety endpoints is added to better evaluate the safety profile of revised dose and regimen.

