3.2 ENDPOINTS

3.2.1 Efficacy endpoints

Annualized bleeding rate (ABR) during the efficacy period

Annualized spontaneous bleeding rate during the efficacy period

Annualized joint bleeding rate during the efficacy period

Time intervals between bleeding events

Annualized weight-adjusted consumption of FVIII, FIX and BPA

Quality of life (QoL) measured by EuroQol 5-dimension 5-level (EQ-5D-5L) score

QoL measured by Haem-A-QoL score.

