- Onset period: The onset period is defined as the period of time consisting of the first 28 days: Treatment Day 1 to Treatment Day 28 (of TDR14767(ALN-AT3SC-001) and LTE14762) (see above - definition of “Treatment Day”); this is the period of time during which the AT lowering capacity of fitusiran is increasing but has not yet reached therapeutic levels.
- Efficacy period 1: The efficacy period 1 is defined as Treatment Day 29 to earlier of End of study date before the dose pause or the last fitusiran administration date before the dose pause + 28 days, whichever comes first.
- Treatment period 1: The treatment period 1 is defined to be the onset period plus the efficacy period 1.

The revised dose and regimen:

- Dose adjustment period: The dose adjustment period is defined as the dose re-start Day 1 to the earlier of dose re-start Day 168 or the end of study.
- Efficacy period 2: The efficacy period 2 is defined as the dose re-start Day 169 to the end of study visit
- Treatment period 2: The treatment period 2 is defined to be the dose adjustment period plus the efficacy period 2.

All the analysis periods will exclude the period of following intercurrent events to avoid confounding of treatment effect for the primary efficacy analysis based on On-Treatment Strategy:

Intercurrent events:

I. “Dose interruption periods”:

- a. Gap between TDR14767(ALN-AT3SC-001)/ LTE14762 study >28 days and skips at least two doses in the gap: Exclude events occurring on dates starting from the date of the last dose in 001 +29 days to the date of first dose in LTE14762 +28 days and gap duration >84 days.
- b. Clinical hold/dose pause period during LTE14762 study: Exclude events occurring on dates starting from the date of the last dose before dose interruption +29 days to the date of dose resumption +28 days and on-hold duration > 84 days.
 - Dose hold in 2017: The last dose before dose interruption is defined as the last fitusiran administration before 2017 [REDACTED]. The first dose after dose resumption is defined as the first fitusiran administration after 2017 [REDACTED].
 - Voluntary dose pause in 2020: The last dose before dose interruption is defined as the last fitusiran administration before 2020 [REDACTED]. The first dose after dose resumption is defined as the first fitusiran administration after 2021 [REDACTED].

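### The SAP's bleed-free duration has no value for exactly one bleed, and it puts zero-bleed and multi-bleed participants on different scales

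*SAP*

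**What the plan says.** The SAP lists "Time intervals between bleeding events" as an efficacy endpoint (SAP 3.2.1). SAP 6.3.1.2 summarizes it through bleed-free duration (BFD), with two rules.

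- General rule: "Bleed-free duration (BFD) for each participant will be calculated as the time interval between 2 protocol-defined treated bleeding events". Bleeds in excluded intercurrent periods do not count. The maximum per participant is summarized descriptively.
- No bleed in the efficacy period: "the overall duration of the corresponding efficacy period will be the bleed-free duration".

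Protocol 10.2.3 has only the between-bleed form: "Bleed-free duration will be defined as the maximum time intervals between 2 bleeding events and will be analyzed descriptively". It has no rule for zero bleeds or for one. SAP 2.6 deletes the Kaplan-Meier analyses because "The protocol specifies only that the times between successive bleeds be summarized descriptively".

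On the periods, SAP 6.3 states: "The efficacy period 2 is defined as the dose re-start Day 169 to the end of study visit". It adds: "All the analysis periods will exclude the period of following intercurrent events". SAP 6.5 uses maximum BFD again for the 2017 hold and the 2020 pause and adds no rule.

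**The concern.** A participant with exactly one counted bleed has no second bleed to close an interval and is not bleed-free either. Neither rule applies, and someone will have to choose a convention after seeing open-label data.

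The two rules also measure different things. The zero-bleed rule runs from period boundary to period boundary. The rule for two or more bleeds ignores both boundaries. A summary that pools them mixes two scales. At stake is the description of a listed efficacy endpoint, including under the revised regimen, which the study extension was meant to inform.

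**Working it through.** **Is there a rule elsewhere?** None was found. Protocol 10.2.3 needs two bleeds. SAP 5.8 imputes only questionnaire and adverse event data. SAP 6.3 defines periods but does not say that a boundary opens or closes an interval. The remark in SAP 6.3.1.2 about time after the first significant dose limits which data are used; it does not make that dose an endpoint of an interval.

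**Period length.** Protocol Table 3, footnote a, keeps participants on treatment for at least 18 calendar months after re-start: 18 × 365.25/12 ≈ 548 days. Efficacy period 2 starts on Day 169, so its planned minimum is 548 − 168 = 380 days, or about 410 to an End of Study visit 30 days later. Efficacy period 1 is longer. From 08-Oct-2015 (SAP 2.5) or 20 July 2017 (SAP 2.1) to 31Oct2020 (SAP Table 4) is 1,850 or 1,199 days, before exclusions and shorter for early discontinuers.

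**The rule applied to example dates (380 days).**

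| Bleed days | SAP rule | Longest stretch, ends included |
|---|---|---|
| none | 380 | 380 |
| 100 | no value | 380 − 100 = 280 |
| 100, 110 | 10 | 380 − 110 = 270 |
| 10, 370 | 360 | 360 |

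For n uniformly placed bleeds, an end stretch is the longest with probability 2/(n+1), so 2/3 for two bleeds. The expected maximum for two bleeds is 380/3 × 1 = 127 days under the SAP rule, and 380/3 × (1 + 1/2 + 1/3) = 232 days with the ends included.

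**Share with exactly one bleed.** The documents give no on-treatment ABR, so the rates are assumptions. With m = ABR × days/365.25, the share is m·exp(−m) for Poisson and m/(1+m)² for gamma-Poisson with dispersion 1.

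| ABR | m, 380 days | 380 days | 3 years | 4 years |
|---|---|---|---|---|
| 0.5 | 0.520 | 31% / 23% | 33% / 24% | 27% / 22% |
| 1 | 1.040 | 37% / 25% | 15% / 19% | 7% / 16% |
| 2 | 2.081 | 26% / 22% | 1.5% / 12% | 0.3% / 10% |

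(Poisson / gamma-Poisson.)

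**Group median of maximum BFD, 380 days.** Simulation of 200,000 participants per scenario, with one-bleed participants missing under the SAP rule.

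| ABR | Poisson: SAP vs one rule | Gamma-Poisson: SAP vs one rule |
|---|---|---|
| 0.5 | 380 vs 380 | 380 vs 380 |
| 1 | 380 vs 314 | 380 vs 372 |
| 2 | 147 vs 234 | 204 vs 270 |

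The direction can be seen from the shares. At ABR 1 (Poisson), 35.3% have no bleed and 36.8% have one. With the latter missing, the zero-bleed share becomes 0.353/(1 − 0.368) = 56%, so the median is the full period. At ABR 2 it is only 0.125/(1 − 0.260) = 17%, so the median falls among multi-bleed participants, whose end stretches are omitted.

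**Four years (1,461 days).** Uninterrupted, ABR 1 gives about 482 vs 668 (Poisson) and 521 vs 791 (gamma-Poisson). ABR 2 gives 397 vs 450 and 397 vs 558. However, SAP 6.3 excludes the 2017 hold when it lasts more than 84 days. If the one rule cuts stretches there, with a single cut at an assumed day 400 or 600, its median falls at ABR 1 to about 566–579 (Poisson) or 600–656 (gamma-Poisson), and at ABR 2 (Poisson) to 400–411 against the SAP's 397.

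**The case against.** The strongest defense is that leaving out the end stretches follows the protocol. Protocol 10.2.3 and the endpoint's name both refer to intervals between bleeds, and with one bleed no such interval exists. On that view it is enough to state a convention for one bleed and report the counts. This stands in part: the between-bleed interval is the protocol's measure and should be kept. It does not settle the mixed scale. The SAP's own zero-bleed rule, which the protocol lacks, already counts time to the period boundaries.

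A longest-gap measure also need not rank participants by bleed count; ABR does that. Even with the ends included, one bleed on day 190 of 380 scores 190, while bleeds on days 10 and 370 score 360. That is fair. The point is that the groups are measured differently, not that every pair must be ordered by count.

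Three stronger readings are tempting, and the documents do not support them:

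- **That the damage is greatest in efficacy period 2.** This holds only for the one-bleed share, and only at ABR 1 or above. At ABR 1 the uninterrupted 4-year medians differ more than the 380-day ones.
- **That the median is always biased, or biased one way.** At ABR 0.5 over 380 days it does not move, and at ABR 1 (gamma-Poisson) it moves by only 8 days.
- **That the SAP drops one-bleed participants.** It is silent. Their absence is what follows from applying the text literally.

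The consequences are also limited: the study is single-arm, BFD is descriptive, and all data appear in by-patient listings (Protocol 10.2).

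**Conclusion.** The point holds as a defect in the definition of a descriptive efficacy measure. One counted bleed has no value, and values for zero bleeds and for two or more are not on the same scale. Both follow from the text and need no assumption.

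The size does rest on assumptions: ABR 0.5 to 2, Poisson or gamma-Poisson counts with dispersion 1, uniform bleed times and a 380-day period. On these, 22% to 37% of participants have exactly one bleed in efficacy period 2. Over 380 days the group median is unchanged at ABR 0.5, too high by 8 to 66 days at ABR 1, and too low by 66 to 87 days at ABR 2. Over 4 years at ABR 1 and 2 it is too low. That gap shrinks once the 2017 hold cuts the stretches, and at ABR 2 (Poisson) it nearly disappears.

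The ABR analysis and the primary safety objective are unaffected. The definition should be corrected before the final analysis, but the study's main conclusions do not depend on it.

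**What to change.** - In SAP 6.3.1.2, define maximum BFD for every participant as the longest of three kinds of stretch: efficacy period start to first counted bleed, between consecutive counted bleeds, and last counted bleed to period end. The same rule then covers 0, 1 and 2 or more bleeds.
- State one treatment of excluded intercurrent windows (whether a stretch is cut there or carried across) and apply it to everyone, including those with no bleed. The SAP does not say this now.
- Report the numbers with 0, 1 and 2 or more bleeds. Keep the protocol's between-bleed interval alongside for those with 2 or more.
- Use the same definition in SAP 6.5 and record the change from Protocol 10.2.3 in SAP 2.7.

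The cost is SAP wording, a small derivation change and one entry in SAP 2.7; no new data are needed. There are three downsides. Values will differ from earlier output that used the present rule. An end stretch is a minimum, because the period boundary cuts it; this is already true of the zero-bleed rule. If stretches are cut at excluded windows, a zero-bleed participant with a mid-period window loses the full-period value. For example, a 3-day minor-surgery window in the middle of 380 days leaves (380 − 3)/2 ≈ 189 days, below the 280 days for one bleed on day 100. That would change the current zero-bleed rule, so the choice should be made openly.
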